
### **C13b. Qualitative and Mixed Method Data Analysis Plan**

**Overview.** Mixed methods will be used to integrate findings from Aim 2 using a quantitative + qualitative structure (wherein both types of data are collected simultaneously) to achieve the function of data expansion for the purposes of evaluation and elaboration (Palinkas et al., 2011). We will use a connecting process (whereby the datasets build upon one another) and work closely with our mixed methods expert ([name]). Rapid ethnography (Millen, 2000) will be used to synthesize the needs assessment data only in the tailored condition to characterize participant experiences. Focus groups will be analyzed separately to characterize participant responses within each site, across conditions. Graduate student researcher ([name]), who was trained in qualitative inquiry methods during the pilot studies, will work with the postdoctoral fellow to train research assistants to identify and code analyzable units of meaning in the focus group transcripts. An iterative approach to coding will resolve disagreements through research team discussion. Inductive analyses based on emergent themes rooted in grounded theory will be conducted (using QSR N-Vivo software). Codes will also be assigned based on contextual factors using [name] et al.'s (2008) Framework of Dissemination. The final list of consensus codes will include themes established *a priori* and through emergent themes analysis.

Using the U.S. NIH guidelines for mixed methods best practices (Creswell, et al., 2011), we will connect the quantitative and qualitative datasets in QSR N-Vivo to allow for case-specific pattern identification and hypothesis testing. For example, we will enter clinician-specific MBC fidelity data

(categorized as “none”, “low”, “moderate”, “high”) and query each qualitative theme for matched clinician focus group quotes in order to investigate the influence of contextual factors on level of MBC fidelity. Based on pilot study qualitative findings, we anticipate that focus groups will yield both positive and negative valenced statements for each of the a priori and emergent themes. We will investigate the extent to which differences exist in the valence of contextual themes between conditions. This approach will allow us to distinguish factors that might explain the differences in the quantitative findings, and notably MBC fidelity.

#### **C14. Potential Problems & Alternative Strategies.**

Our hypothesis is that tailored implementation will outperform the standardized approach. However, it is possible that this hypothesis will not be supported. Findings of this nature would not be undesirable, but rather would illustrate that while emerging research suggests the need to contextualize implementation interventions (Fixsen, 2005; Wallerstein & Duran, 2010), this customization compromises ultimate outcomes—a critical realization for the field of implementation science. Furthermore, if we are unable to detect mediators of implementation and effectiveness outcomes included in this proposal, it may suggest the need to re-evaluate the *Framework of Dissemination*. Specifically, putative mediators of the dissemination and implementation process not included in this model might require empirical investigation. Our qualitative analyses will allow for careful examination of unanticipated mediators. At the level of the clinician, we anticipate substantial variability in competency and general approach to psychotherapy. However, we are not concerned about the effects of this variability on study outcomes because (1) randomization should result in equivalent variability across conditions and (2) MBC is conceptualized as transtheoretically relevant, regardless of the therapist’s orientation or training.

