We propose a randomized trial of standardized versus tailored MBC implementation in Centerstone, one of the nation's largest not-for-profit community mental health centers. This proposal builds on a 2-year academic-community partnership in which the long-term goal is to introduce MBC across 100+ sites. This hybrid type 2 design will assess both implementation (clinician-level; MBC fidelity) and intervention (client-level; depression severity) outcomes. We have the unique opportunity to evaluate MBC implementation, as Centerstone will have recently introduced a new electronic health record (EHR) system. The implementation protocol is informed by our 2-site pilot study in which MBC achieved 67% penetration. The Patient Health Questionnaire (PHQ-9; [name], 2001) will be embedded in the EHR using tablet computer client data capture. Both conditions will use a blended implementation protocol of the best available evidence-based strategies to ensure equal access to resources, including (a) a needs assessment, (b) formation of an implementation team, (c) MBC use guidelines, (d) training, and (e) triweekly group consultation. [name] et al.'s (2008) Framework for Dissemination will guide evaluation (needs assessment, implementation, and outcome evaluation). This framework will also be used to tailor training and consultation content to target barriers identified in the needs assessment (contextual factors, e.g., attitudes); the standardized condition content is set *a priori*. In the tailored condition, the implementation team will establish the MBC use guideline (e.g., monthly administration), whereas the standardized condition guideline will require routine administration prior to each session with a depressed client (Lambert et al., 2003). This design will test the Dynamic Sustainability Framework (Chambers, et al., 2013), as sites in the tailored condition will adapt MBC guidelines to fit their context. MBC fidelity (range 0-3; client completed=0/1; clinician reviewed=0/1, scores discussed=0/1) and reasons for deviations (e.g., lack of time) will be monitored via EHR enhancements; clients will also report on clinician discussion of scores.

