Phase 1: Pre-Implementation (Months 0-8). The PHQ-9 and fidelity measures will be embedded in the EHR and the PHQ-9 linked to tablet computers for client completion to promote feasibility. Phase 2: Randomized Implementation Trial: Dynamic Waitlist Control (Months 8-38; Sites:  $N=12$ ; Clinicians:  $N=150$ ; Clients:  $N=500$ ; mixed within- & between-subjects design). MBC implementation will occur across 4 cohorts (2-4 sites) at early and later stages (each with 5-months active implementation, 10-months sustainment) to reduce confounds (timing) and increase feasibility (phased training). Both conditions will enact the 5 strategies within the active implementation period. We will use rapid ethnography (month 1) to synthesize the needs assessment data and develop the tailored content. Phase 3: Characterization of MBC Fidelity (Months 38-48). MBC fidelity will be coded, clinician and client fidelity reports will be triangulated, and sustainment will be evaluated.

**Specific Aims.** The hybrid design yields one co-primary aim (outcomes at the clinician- and client-levels) and two secondary exploratory aims in the context of a pragmatic trial (Thorpe et al., 2009).

**Aim 1:** To compare the effect of standardized versus tailored MBC implementation on clinician-level (**1a**) and client-level (**1b**) outcomes. We hypothesize that tailored implementation will outperform standardized in terms of (**H1a**) MBC fidelity, and (**H1b**) reducing client depression severity.

**Aim 2:** To identify contextual mediators of MBC fidelity. We hypothesize (**H2**) that contextual mediators (structure, norms, etc.) will be leveraged in the tailored condition, but serve as barriers in the standardized condition.

**Aim 3:** To explore the impact of MBC fidelity on client outcomes (Chambers et al. 2013). We hypothesize (**H3**) that adapted MBC protocols (tailored condition) will outperform weekly administration of PHQ-9s (standardized condition) with respect to clinically significant change in depression severity from intake to week 12.

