**Table 1. Implementation Conditions**

Standardized	Tailored
Manualized implementation content	Content adapted by implementation team to address barriers
Developed a priori	Responsive to local needs
Standardized MBC guide	MBC administration set by site

to improving care not necessarily focused on EBP integration (Baker, 2006). This proposal reflects a movement in the field (e.g., Dynamic Adaptation Process; Aarons, et al., 2012) to consider planned adaptations of the EBP and systems/organizations to promote EBP integration and sustainment.

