## **C. APPROACH**

**Overview.** Given the underwhelming use of MBC in community mental health settings coupled with the demand for performance outcome assessment (Affordable Care Act), this randomized implementation trial aims to compare the effectiveness of a standardized versus tailored approach to implementation of MBC with co-primary outcomes at the clinician (MBC fidelity) and client (depression severity) levels. We will randomize 12 sites of a large community mental health center (Centerstone) to early or later stage standardized or tailored implementation enrolling 150 clinicians and 500 depressed clients in a pragmatic trial (Thorpe et al., 2009). The main clinician level outcome is MBC fidelity, defined as (a) client completion of the PHQ-9, (b) clinician review of scores in the electronic health record, and (c) discussion of scores in session. Phase 1 (months 0-8) will interface the most widely used and validated depressive symptom severity measure (Patient Health Questionnaire-9 item; PHQ-9; [name], 2001) with the electronic health record; this measure is the main client level outcome. Phase 2 (months 8-38) constitutes the active implementation (5 months) and sustainment (10 months) phase. In both conditions, clients will have the option to complete the PHQ-9 on tablets in the waiting room prior to session, which will feed scores to clinicians via the electronic health record. Sites randomized to the standardized condition will begin with a baseline mixed methods needs assessment (for the purposes of putative mediator data collection) and receive the guideline that MBC is to be used in each session with a depressed client. The standardized condition will include manualized training and triweekly group consultation with experts to promote MBC fidelity and optimize its clinical utility. An implementation team (including a site administrator, opinion leader, MBC champion, and research personnel) will convene prior to each triweekly group consultation to review progress and troubleshoot problems. Sites randomized to the tailored condition will also begin with a needs assessment to identify contextual factors that may serve as barriers to the implementation (guided by the *Framework for Dissemination*; [name] et al., 2008; see C7). Training and triweekly group consultation will be tailored to address these barriers (e.g., clinician attitudes toward MBC). The implementation team (same composition as in standardized) will define a site-specific guideline for MBC use (e.g., monthly) and convene prior to each triweekly group consultation to troubleshoot MBC fidelity barriers. At the start of the active implementation across both conditions, depressed clients of participating clinicians will be enrolled to compare the effect of standardized versus tailored MBC implementation on client outcomes. Phase 3 (months 38-48) will characterize MBC fidelity using electronic health record data capture. The evaluation approach is guided by the *Framework for Dissemination* ([name] et al., 2008) and includes a baseline needs assessment, implementation/process evaluation (5 months into implementation), and outcome/impact evaluation (15 months into implementation). This design will allow for a direct test of the assumption that voltage drop in treatment outcomes occurs in the context of adapting the intervention to fit the context (Chambers et al., 2014), while simultaneously exploring the effect of standardized and tailored approaches to MBC implementation.

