**Figure 1. Framework for Dissemination**

**C8. Complementary Testable Model.** Chambers, Glasgow, and Stange (2013) recently put forth the Dynamic Sustainability Framework to promote testing of falsifiable hypotheses that program drift from "fidelity" of evidence-based practices leads to a voltage drop in implementation outcomes as compared to effect sizes observed in efficacy trials. Chambers et al. (2013) contend that an alternative hypothesis is important to consider: intentional adaptations to EBP implementation that are informed by community

stakeholders and account for relevant multi-level contextual factors may optimize sustainment and intended outcomes. This proposal intends to test this model. Specifically, the standardized condition requires (via a guideline) that MBC be implemented weekly prior to each psychotherapy session according to its documented efficacy (e.g., Bickman et al., 2008; Whipple et al., 2003). Conversely, the tailored condition will allow the implementation team at each site to adapt this guideline, taking into account their specific context (e.g., monthly MBC implementation).

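### A failed superiority test would not show that tailoring compromises outcomes, and the arm contrast tests a whole package rather than adaptation of the intervention

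*Combined protocol and SAP*

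**What the plan says.** Two parts of the combined protocol and SAP matter here.

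**Reading of an unsupported hypothesis.** The Specific Aims set a superiority hypothesis: "We hypothesize that tailored implementation will outperform standardized in terms of" MBC fidelity (H1a) and client depression severity (H1b). Section C14 concedes that "it is possible that this hypothesis will not be supported" and then says what such findings would illustrate: that "this customization compromises ultimate outcomes—a critical realization for the field of implementation science". It does not separate an inconclusive result from one that favours the standardized arm. The quantitative analysis plan (C13a) has no non-inferiority or equivalence margin and no rule for reading confidence intervals.

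**What the arm contrast is said to test.** The Overview in section C states: "This design will allow for a direct test of the assumption that voltage drop in treatment outcomes occurs in the context of adapting the intervention". Section C8 describes the hypothesis under test as one in which drift from fidelity "leads to a voltage drop in implementation outcomes as compared to effect sizes observed in efficacy trials". The arms differ in two ways. In the tailored arm, Table 1 lists "Content adapted by implementation team to address barriers", and the Specific Aims use the framework to "tailor training and consultation content to target barriers identified in the needs assessment". The tailored sites also set their own PHQ-9 guideline, whereas the standardized guideline is every session (Tables 1 and 3). Section C15 speaks of comparing the adapted use of MBC with the empirically supported approach.

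**The concern.** These are two separate points.

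First, not showing that tailored is better is different from showing that it is worse. C14 is the only place where the plan says how an unsupported hypothesis would be understood, and it goes straight to harm. Used as the guide to interpretation, it would let an inconclusive trial be cited as evidence against adapting care to sites.

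Second, if the arms do differ, the difference belongs to everything that separates them. Barrier-targeted training, consultation and team work change together with the PHQ-9 schedule, so no result can be assigned to the schedule or to adaptation of MBC itself. A gain from better implementation and a loss from sparser measurement could also offset each other. And if voltage drop means a shortfall against efficacy-trial effects, a comparison of two MBC arms does not measure it.

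**Working it through.** **Inputs (C13a, power calculations).** Two-sided alpha .05; power 80% (printed as > 80); detectable d = .46 for clinicians (N = 150) and d = .30 for clients (N = 500); site ICC .05. There are 12 sites, half per condition (C11).

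**Reproducing the plan's figures.** They come from a growth-model simulation whose slope variances, number of waves and effect coding are not given, so it cannot be rerun. A closed form is 2.80 × sqrt(4 × DE / N), with DE = 1 + (N/12 − 1) × ICC.

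- Clinician, ICC 0: 0.457. ICC .05: DE = 1.575, giving 0.574 (0.637 with t on 10 df).
- Client, ICC 0: 0.251. ICC .05: DE = 3.033, giving 0.436 (0.484 with t on 10 df).

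Neither ICC value gives both stated figures. With the simulation inputs missing, this does not show them to be wrong, so they are taken as stated below.

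**How often superiority would not be shown.** At the detectable size the standardized effect is 1.96 + 0.84 = 2.80. Let k be the true tailored benefit as a fraction of the detectable size. Then:

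- P(superiority not shown) = Phi(1.96 − 2.80k)
- P(95% interval wholly on the worse side) = Phi(−1.96 − 2.80k)

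| k | True benefit (client / clinician) | Superiority not shown | Interval wholly worse |
|---|---|---|---|
| 0 | 0 / 0 | Phi(1.96) = 97.5% | 2.5% |
| 0.5 | .15 / .23 | Phi(0.56) = 71% | 0.04% |
| 1 | .30 / .46 | Phi(−0.84) = 20% | about 0 |

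**Sensitivity.** Using site ICC .05 with 12 sites instead of the stated detectable sizes, superiority is missed in 51 to 59% of trials at client d = .30 and in 39 to 47% at clinician d = .46 (normal, then t on 10 df).

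**Interval width.** The client standard error implied by the plan is .30 / 2.80 = 0.107, so the 95% half-width is 1.96 × 0.107 = 0.21. For clinicians it is 1.96 × (.46 / 2.80) = 0.32. An estimate near zero would be compatible with benefit as well as harm.

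**Attribution.** No arithmetic applies. Table 3 gives a different focus by condition for the implementation team, guideline, training and consultation; only the tablet and progress-note rows are the same. Every randomised contrast therefore carries all four differences. The Aim 3 model adds counts of sessions held and of sessions with the PHQ-9 recorded or discussed. These arise after randomisation and do not separate the components. No efficacy-trial benchmark appears in C13a, and both arms receive MBC.

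**The case against.** The strongest reply is that C14 is one sentence of discussion in a grant narrative. C13a contains no rule equating non-significance with harm, testing is two-tailed, and section B1 asks neutrally which approach does better. That stands: nothing commits the investigators to publish a harm claim. But nothing in C13a overrides the sentence either.

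A reader might infer that a true tailored benefit would often be reported as harm. The documents do not support that. At the plan's own detectable sizes the miss rate is 20% per outcome. The higher rates need smaller effects, and C12a says only that a small effect is predicted, without a number, or they need the closed-form ICC calculation. The harm report would also follow only if C14 were applied as the reporting rule. A significant result in the wrong direction, given a true benefit, had probability at most 0.6% in every case computed.

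A reader might also infer that bundling is what turns a null into harm. It is not. Bundling blocks attribution and allows cancellation; the C14 wording alone makes the step to harm.

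It is fair, too, that sections B2 and C10 define tailoring as matched content with room to change the intervention, so a package comparison is a legitimate aim. Only the language about adapting the intervention goes too far. Section C15 does not itself claim a direct test; it needs consistency, not retraction.

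Finally, the percentages are not operating characteristics of the planned fidelity analysis. C13a models two binary outcomes and chooses among models by BIC, so the selected model may contain no group term. That stands and shapes the fix.

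**Conclusion.** Both points hold, separately. C14 draws a conclusion of compromise that a failed superiority test cannot support. If the arms truly did not differ, that reading would be triggered in 97.5% of trials, and with a true benefit of half or all of the detectable size in about 71% or 20%. These figures assume a normal-theory two-sided .05 test and the plan's stated detectable sizes at exactly 80% power; the half-size effect is illustrative.

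The direct-test claim in the Overview overreaches because the arms differ in content as well as schedule, and because voltage drop as defined in C8 needs a benchmark that the analysis does not contain. This limits what may be concluded; it does not invalidate the randomised comparison of the two packages.

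**What to change.** 1. **C14.** State that customization compromised an outcome only if the 95% confidence interval for tailored versus standardized lies entirely on the worse side (lower fidelity, or less improvement in PHQ-9). Otherwise report *superiority not shown*, with the interval and the largest tailored deficit it still allows.
2. **C13a.** Report the group contrast and interval for each co-primary outcome even if BIC drops the group term. If group × time is kept, name the time point of the contrast in advance.
3. **Overview in section C.** Replace the direct-test claim with a randomised comparison of the tailored package (content plus site-set schedule) against the standardized package. Bring C15's wording on adapted use into line.
4. **Schedule alone.** Label any statement about PHQ-9 frequency by itself as non-randomised and exploratory.

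The cost is rewording and a named contrast per outcome, with no new data or sites. The downside is that a null result would support a weaker statement than the one now promised.

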#### **C15. Justification & Feasibility.**

We selected an effectiveness-implementation hybrid to investigate one co-primary aim that focuses on (1) implementation outcomes at the clinician level and (2) effectiveness with respect to client outcomes. To test the Dynamic Sustainability Framework (Chambers et al., 2013), we will need to compare the clinical effectiveness of the adapted use of MBC (tailored) as compared to the empirically supported MBC approach (standardized). Simultaneously, because no studies have attempted to scale up MBC in community mental health, we need to evaluate the implementation (clinician-level: fidelity) outcomes. The effectiveness-implementation hybrid design type 2 was identified as the optimal and innovative design solution for this proposal.

Within the effectiveness-implementation hybrid design, we will randomize sites to condition using a dynamic waitlist controlled approach. Half of the sites will receive a standardized approach to implementation and the other half will receive a tailored approach. This design reduces the effect of management- or clinician-level readiness or client factors that might otherwise confound the training effects allowing for unbiased data (Brown, et al., 2006). This design also affords the opportunity to conduct blocking on smaller time units and statistically provides large gains in efficiency (range from 33 to 100% gains). Moreover, training efficiency is achieved as not all sites must be trained at once, therefore allowing the same trainer(s) to train all sites to reduce any possible effect at the level of trainer expertise (Herschell, Kolko, Baumann, & Davis, 2010).

We have already piloted many of the implementation strategies and the evaluation approach (*C8: Pilot Studies*). Moreover, Centerstone has successfully completed >150 studies since 2003; two of these studies were NIMH-sponsored (CATIE, Keefe et al., 2007; STAR\*D, Insel, 2006), whereas others involved wide-scale implementation of EBPs for SAMHSA-sponsored program evaluations. Co-I ([name]) has coordinated many of these multi-site clinical trials at Centerstone. This proposal’s design considerations and the established strong collaborative relationship of our investigative team, we have no concerns regarding this proposal’s feasibility.

